## 2. Randomization

Block randomization via computer-generated sequence. Allocation concealed until participant assignment.

## 3. Analysis Methods

Baseline Characteristics: Independent t-tests or chi-square

Primary Outcome (Anxiety): Independent samples t-test

Secondary Outcomes:

- Health literacy, satisfaction, technology acceptance: t-tests
- Associations: One-way ANOVA and chi-square tests

Software Used: SPSS v25

Missing Data: Excluded from per-protocol; ITT analysis with multiple imputation recommended in future studies

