## **6. Outcomes**

Primary: Hamilton Anxiety Rating Scale (HAMA)

Secondary: Health Literacy Questionnaire (HLQ), Satisfaction (adapted Black et al.), Technology Acceptance

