## 1. Sample Size Calculation

Using G\*Power with a medium effect size ( $d = 0.5$ ), alpha = 0.05, power = 0.80. Minimum of 64 participants required. Target recruitment: 80 (to allow for dropouts).

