## 4. Significance Level

Two-tailed tests with  $\alpha = 0.05$ .

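### Is the unadjusted t-test for the primary anxiety score a fault, because adjusting for a pre-session score would be more precise?

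*Protocol*

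**What the plan says.** The protocol restarts its section numbering for the statistical part, so sections are named here by heading.

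- **Analysis Methods** sets the primary test: "Primary Outcome (Anxiety): Independent samples t-test". It does not say whether the test is on the final score or on change.
- **Analysis Methods** also has a line on starting values, "Baseline Characteristics: Independent t-tests or chi-square", which lists no variables.
- **Outcomes** names the scale, "Primary: Hamilton Anxiety Rating Scale (HAMA"), and gives no time of measurement.
- **Intervention** describes a single 30-minute session and no assessment schedule.
- **Sample Size Calculation** uses a standardised difference of 0.5 with "alpha = 0.05, power = 0.80" and concludes "Minimum of 64 participants required. Target recruitment: 80 (to allow for dropouts").
- **Significance Level** adds "Two-tailed tests".

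**The concern.** The trial is small and has one primary comparison. The objective is whether education lowers anxiety, which makes a before-and-after measurement plausible, and baseline characteristics are to be compared in any case. If a pre-session HAMA is on file, an unadjusted test of final scores ignores the covariate most likely to predict the outcome. ANCOVA could then give a narrower confidence interval from the same women, and the named software can fit it. At stake is precision only. Neither bias nor the false-positive rate is in question.

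**Working it through.** **Inputs from the protocol.** d = 0.5, α = 0.05, power 0.80, minimum 64 and target 80 (Sample Size Calculation); two-sided testing (Significance Level).

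**Inputs that must be assumed.** 1:1 allocation (Randomization mentions blocks but no ratio), normal scores, a t-test on final scores, and a pre/post correlation r, taken over a range from 0 to 0.7.

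**1. The plan's own figure.** Power comes from the noncentral t distribution with 2n − 2 degrees of freedom and noncentrality d√(n/2), where n is the number per arm.

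- n = 64 per arm: 0.5 × √32 = 2.83, power 0.801
- n = 40 per arm (80 in total): 0.5 × √20 = 2.24, power 0.598
- n = 32 per arm (64 in total): 0.5 × √16 = 2.00, power 0.504

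The stated 64 is therefore reproduced as a per-arm number, 128 in total. That is a separate matter. It is used here only to fix the reference power of the t-test at 60% (N = 80) and 50% (N = 64).

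**2. Break-even correlation.** With equal arms and a normal covariate,

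Var(ANCOVA) / Var(final-score t-test) = (1 − r²)(N − 3)/(N − 4).

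Setting this to 1 gives r = 1/√(N − 3):

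- N = 80: 1/√77 = 0.114
- N = 64: 1/√61 = 0.128

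Allowing also for the degree of freedom lost in the critical value gives 0.116 and 0.131.

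**3. Size of the gain, if a pre-session score exists.**

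| r (assumed) | Variance ratio, N = 80 | ANCOVA power, N = 80 | Variance ratio, N = 64 | ANCOVA power, N = 64 |
|---|---|---|---|---|
| 0 | 1.01 | 59% | 1.02 | 50% |
| 0.1 | 1.00 | 60% | 1.01 | 50% |
| 0.3 | 0.92 | 63% | 0.93 | 53% |
| 0.5 | 0.76 | 72% | 0.76 | 62% |
| 0.7 | 0.52 | 87% | 0.52 | 78% |

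The result runs from a negligible loss to a gain of 27 to 28 points, depending entirely on r. These are averages. In simulation at r = 0.3, the ANCOVA interval was still the wider of the two in 11% of trials with 80 women and 16% with 64.

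**4. Dependence on the comparator.** Where a pre-session score exists, the planned t-test could equally be on change. With equal variances before and after, the variance of the change comparison relative to the final-score comparison is 2(1 − r). For N = 80:

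- r = 0.7: 2 × 0.3 = 0.60; noncentrality 2.24/√0.60 = 2.89; power about 81%. ANCOVA's standard error is √(0.517/0.60) = 0.93 of this, so its interval is about 7% narrower. Against the final-score test it is 28% narrower.
- r = 0.5: 2 × 0.5 = 1.00; the two t-tests coincide at 60%.
- r = 0.3: 2 × 0.7 = 1.40; noncentrality 2.24/√1.40 = 1.89; power about 46%, against 63% for ANCOVA.

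ANCOVA does better on either reading at these correlations, but the size of its advantage cannot be read from the protocol.

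**5. Validity of the planned test.** Simulated with no treatment effect, for r from 0 to 0.7, the t-test and ANCOVA each rejected in 4.9% to 5.2% of trials. Randomisation makes the unadjusted difference unbiased.

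**6. Is the condition met?** Outcomes gives a scale without a time, Intervention gives a session without an assessment schedule, and the baseline line names no variable. None of these establishes a pre-session HAMA, and none rules it out.

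**The case for a change.** The best argument for keeping the point is that the protocol does not leave the method open. It names a test, next to the sample size and significance level, so the choice is fair to examine. The trade is also lopsided: at worst the mean interval widens by less than 1% (0.7% with 80 women and 0.8% with 64, at r = 0), while at r = 0.5 it narrows by about 13% and power rises by 11 to 12 points. The advice would be conditional, would add no assessment, and could keep the t-test as supportive. The investigators could settle the condition at once.

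The arithmetic in this stands. The step to a fault does not. Advice to switch if the score exists and otherwise change nothing identifies no defect in the text. A preference among valid tests is not an error, and measurement times and covariate adjustment are commonly left to an analysis plan, which is not shown here. Nor is the change certain to be costless. Study Design dates the trial from November 2023 to January 2024, and Ethics reports consent as already obtained, so the text may have been written during or after conduct. That is an inference, but replacing the primary test after outcomes had been seen would be a post hoc change.

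**Conclusion.** The concern does not hold. The planned t-test is valid and unbiased under randomisation, keeps its nominal error rate, and conflicts with nothing else in the protocol. The possible gain is real in principle: it begins at a correlation of about 0.114 (80 women) or 0.128 (64), and at 80 women it is worth about 3 points of power at 0.3 and 12 at 0.5. Those figures rest on 1:1 allocation, normal scores, a final-score comparison and an assumed correlation. Above all, they rest on a pre-session HAMA that the protocol does not mention. Adjustment would not settle the sample-size question either: with 80 women and a final-score comparison, ANCOVA has about 78% power at r = 0.6, so 80% needs a correlation somewhat above that. No change to the plan follows from this point.

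### Do the planned association tests force scores to be cut into categories and make chance findings likely?

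*Protocol*

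**What the plan says.** In the Protocol's section 3, Analysis Methods, anxiety as the primary outcome has one independent-samples t-test. Two lines follow under the secondary outcomes: "Health literacy, satisfaction, technology acceptance: t-tests" and, separately, "Associations: One-way ANOVA and chi-square tests". The second line names no outcome, no grouping factor and no number of tests. For baseline characteristics the same section names either a t-test or a chi-square test.

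Section 4, Significance Level, reads "Two-tailed tests with" α = 0.05. It gives no adjustment or ordering for secondary tests.

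Section 2, Study Objectives, lists the effect on three secondary outcomes and no objective about associations. Section 3, Study Design, has two arms. Nothing in the document says that a score will be categorised.

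**The concern.** The t-test line treats health literacy, satisfaction and technology acceptance as continuous scores. The next line brings in chi-square, a test for categories. Read together, they suggest that the same scores will be split at cut-points not yet chosen. That would waste information in a small trial and let the choice of cut influence the result.

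One-way ANOVA looks odd as well. Across two arms it only repeats the t-test (F = t²). Across a participant characteristic, no term for arm is mentioned.

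Finally, an open-ended set of tests, each at 0.05 and listed under the secondary outcomes, could produce a significant result by chance that is then reported beside the randomised comparisons.

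**Working it through.** **Inputs.** From the Protocol: α = 0.05 two-sided (section 4, Significance Level); one primary t-test, three secondary t-tests and an uncounted set of association tests (section 3, Analysis Methods); a recruitment target of 80 (section 1, Sample Size Calculation). The plan gives no error rate or test count for the associations, so there is no figure of its own to reproduce on this point.

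**Step 1: does the wording require categorised scores?** One-way ANOVA needs a continuous outcome and a categorical factor, so a score can enter uncut. Chi-square needs two categorical variables, and variables collected as categories can supply both. A score has to be cut only if it enters a chi-square test itself or serves as the ANOVA factor. The document says neither. The baseline line in the same section, t-test or chi-square, reads naturally as choosing the test by type of variable, and the associations line can be read the same way. Nor does testing at 0.05 imply any categorising.

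**Step 2: what would a median split cost?** For a normal score the information kept is 2/π = 0.637, and 80 × 0.637 = 50.9. In a simulation of 20,000 trials with a standardised difference of 0.5 and 40 women per arm (1:1 allocation assumed), power was about 60% for the t-test and 40% after a median split with chi-square. The loss is real, but it applies only if a split is made, and none is planned.

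**Step 3: how likely is a chance finding?** With k independent tests and all nulls true, the chance of at least one false positive is 1 − 0.95^k, and the expected number is 0.05k.

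| Set of tests | k | Expected | At least one |
|---|---|---|---|
| Three secondary t-tests | 3 | 0.15 | 14.3% |
| Plus one ANOVA and one chi-square | 5 | 0.25 | 22.6% |
| Further counts, for scale | 10 | 0.50 | 40.1% |
| | 13 | 0.65 | 48.7% |
| | 14 | 0.70 | 51.2% |
| Assumed: 3 outcomes by 5 characteristics | 15 | 0.75 | 53.7% |
| Assumed: 3 outcomes by 8 characteristics | 24 | 1.20 | 70.8% |

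Only the first row rests on a count in the document. The second is the smallest set that fits the wording. Positive correlation between tests would generally lower the last column; the expected numbers do not depend on correlation.

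**Step 4: is the ANOVA wrong in itself?** The factor is not stated to be arm. If it is a baseline characteristic, randomisation makes arm independent of it in expectation, so leaving arm out of the model costs mainly precision.

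**Step 5: is the primary result affected?** No. Anxiety is the single primary outcome, with one t-test at 0.05. Any inflation concerns secondary claims.

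**The case for a change.** The best argument for a fault is that the plan has already chosen methods and a level without saying what they are for. The association tests answer no stated objective, carry no exploratory label and sit under the secondary outcomes at the same 0.05 as the randomised comparisons. Even the smallest reading gives 22.6%, more than four times 5%. Three outcomes crossed with five to eight characteristics would not be an unusual set. Section numbering also restarts at the sample size section, so these pages may be the statistical plan itself.

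Part of this stands. The line is vague, it matches no objective, and a short clarification would help a reader. But vagueness is not a wrong statement. The variables, the status of the tests and any multiplicity rule for secondary outcomes are commonly set in a separate statistical analysis plan, which may exist and is not at hand; the numbering cannot settle that. A later plan could limit chi-square to categorical variables and call the associations exploratory without contradicting anything written here. Applying Holm to the secondary t-tests, barring significance claims, or using linear models adjusted for arm are reasonable preferences, but statisticians differ on them and they correct no stated error.

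**Conclusion.** The concern does not hold. Nothing in the Protocol requires or announces that scores be cut, so the loss of information has no planned analysis to attach to. That chance findings are likely depends on an assumed 15 to 24 independent null association tests. The document itself supports 14.3% for its three named secondary t-tests and, on the smallest reading of the associations line, 22.6% for five, both under independence with all nulls true. The primary comparison keeps its own 0.05. What is left is unspecified detail of a kind that a protocol may leave to its analysis plan. The judgement would change if an analysis plan categorised these scores, or presented a large set of association tests as confirmatory.

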## 2. Study Objectives

- Primary Objective: To evaluate whether robot-assisted digital education reduces anxiety among pregnant women with GDM.
- Secondary Objectives: To examine the impact on health literacy, satisfaction with health education, and acceptance of digital technologies.

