## 3. Study Design

Type: Randomized Controlled Trial (RCT)

Setting: Obstetrics outpatient clinic of a regional hospital in Taiwan

Duration: November 2023 to January 2024

Groups:

- Experimental group: Robot-assisted education
- Control group: Tablet-based video education

Blinding: Single-blind (participant and assessor)

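### The only analysis stated is per-protocol with missing data excluded; analysis by intention to treat is put off to future studies, although the trial is randomised and plans for dropouts

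*Protocol*

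**What the plan says.** The protocol has one line on who is analysed and what happens to missing data, in 3. Analysis Methods: "Missing Data: Excluded from per-protocol; ITT analysis with multiple imputation recommended in future studies". The line for the primary outcome in the same section, "Primary Outcome (Anxiety): Independent samples t-test", names no population. No other section names an intention-to-treat, full-analysis or modified intention-to-treat set.

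Three other places bear on this:

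- 2. Study Objectives states a causal aim: "To evaluate whether robot-assisted digital education reduces anxiety among pregnant women with GDM".
- 3. Study Design calls the study a randomised controlled trial, and 2. Randomization describes how: "Block randomization via computer-generated sequence", with concealed allocation.
- 1. Sample Size Calculation expects losses: "Minimum of 64 participants required", then "Target recruitment: 80 (to allow for dropouts".

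**The concern.** Randomisation supports a causal reading of the anxiety difference only while women are compared in the groups to which they were allocated. A per-protocol analysis without missing data drops women because of events after allocation. If those events differ between the robot and tablet arms and are related to anxiety, the remaining groups differ for reasons other than the education they received.

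The protocol foresees dropouts, then commits to the analysis that is most exposed to them. It names the more robust approach only as advice for other studies. As written, no result would use all the randomised women, and nothing would show how far the conclusion depends on those left out.

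**Working it through.** **1. The passages side by side.** The aim is causal, the design is randomised with concealed allocation, and losses are budgeted for. The only analysis set named is per-protocol without missing data, and the set that would match the aim and design is assigned to later research. The line does not stay silent or refer to another document: it says what is done here and what is not.

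**2. The implied loss allowance.** Inputs are 64 and 80, from 1. Sample Size Calculation.

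- (80 − 64)/80 = 16/80 = 20%, and 64/(1 − 0.20) = 80.

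The protocol states no dropout rate; 20% is the margin its two figures imply across both arms. Separately, for d = 0.5 with "alpha = 0.05, power = 0.80" and a two-sided two-sample t-test, the exact calculation gives 63.8, so 64 per arm (128 in total). The figure of 64 therefore reproduces per arm and not as a total. That is a different matter, and this point does not depend on it.

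**3. How large the bias could be.** The documents give no loss pattern, so everything here is assumed:

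- 40 per arm (80 split equally; the allocation ratio is not stated);
- anxiety score standardised to N(0,1), with no true effect;
- each woman lost independently, with logit P(lost) = a + b × score, where b = 0.5 or 1.0 per SD and a is set to give the stated mean loss;
- equal or heavier loss in the robot arm;
- pooled two-sided t-test at 0.05 on the women who remain.

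Bias is the mean score of the remaining robot women minus that of the remaining tablet women, by numerical integration. A negative value favours the robot. Type I error comes from 40,000 simulated trials per case, with a Monte Carlo standard error of about 0.1 to 0.2 points.

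| Loss, tablet vs robot | Bias in SD, b = 0.5 / 1.0 | Type I error, b = 0.5 / 1.0 |
|---|---|---|
| 0% vs 20% | −0.096 / −0.173 | 6.8% / 11.2% |
| 10% vs 30% | −0.094 / −0.162 | 6.7% / 10.1% |
| 0% vs 10% | −0.049 / −0.091 | 5.4% / 6.9% |
| 5% vs 15% | −0.048 / −0.085 | 5.5% / 6.4% |
| 10% vs 20% | −0.047 / −0.082 | 5.4% / 6.6% |
| 15% vs 25% | −0.047 / −0.081 | 5.3% / 6.2% |
| 5% vs 10% | −0.024 / −0.044 | 5.2% / 5.3% |
| 20% vs 20% | 0.000 / 0.000 | 4.8% / 5.1% |

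Against the planned d = 0.5, the 20-point cases run from 0.094/0.5 = 19% to 0.173/0.5 = 35%.

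**4. What imputation would recover.** Take the 10% vs 30% case and impute by regression within arm on one baseline predictor that has correlation r with the score. Percentages are taken before rounding.

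| r | Remaining bias in SD, b = 0.5 / 1.0 | Share removed |
|---|---|---|
| 0 | −0.09 / −0.16 | 0% |
| 0.3 | −0.09 / −0.15 | 8–9% |
| 0.5 | −0.07 / −0.13 | 22–24% |
| 0.7 | −0.05 / −0.09 | 44–48% |

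This is the hard case, in which loss depends on the outcome itself. If loss depends only on the predictor (r = 0.5), the bias of −0.048 / −0.080 falls to about 0.

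**The case against.** The strongest reply has four parts.

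- **The link to the primary test is inferred.** The primary-outcome line names no population, and the missing-data line is loosely worded. This is true. But per-protocol is the only set mentioned and intention to treat is explicitly deferred, so no other reading is offered.
- **The loss patterns are not in the document.** The 20% is a recruitment margin over both arms, not a difference between them. The intervention is one 30-minute session, and no later visit is described, so loss may be small. At 5% vs 10% the error rate is practically nominal. This stands: the harm is conditional, and the large figures must not be read as a forecast.
- **The illustration covers lost outcomes only.** It does not model the exclusion of women who deviated but have a score, and it is not a measure of what imputation would save, which under outcome-dependent loss is less than half. The protocol names no baseline HAMA, so a strong predictor cannot be assumed. This stands too. For women who deviated but were measured, analysis as allocated restores them completely.
- **Some detail belongs in an analysis plan.** The definition of the per-protocol set, the imputation model, sensitivity analyses and reporting of losses can properly be settled there, and their absence is not the fault raised here.

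None of this meets the central point. A randomised trial that expects dropouts has written down a per-protocol analysis and ruled out the as-randomised one for itself.

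**Conclusion.** The concern holds and should be fixed. The protocol makes a stated choice that, followed as written, can break the randomised comparison for its primary outcome, and it offers no analysis that would reveal this.

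The size cannot be derived from the document. Under the assumptions above, it ranges from nothing (no loss, or equal loss under the same mechanism), through 0.02–0.04 SD with an almost nominal error rate (5% vs 10%), to 0.09–0.17 SD with 6.7–11.2% type I error (a 20-point difference between arms). If nobody is lost or deviates, the per-protocol and as-randomised sets coincide and nothing is at stake. The direction, in favour of the robot, follows from assuming heavier loss of anxious women in that arm; the reverse pattern would reverse it.

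**What to change.** In 3. Analysis Methods, replace the missing-data line with wording such as:

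> The primary analysis includes all randomised participants in the group to which they were allocated, whether or not they adhered. Missing HAMA scores are multiply imputed using group and the baseline variables collected. A per-protocol complete-case analysis is supportive.

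Delete the remark that leaves this to future studies. Two additions are useful but optional: a sensitivity analysis for data missing not at random (for example delta-adjusted imputation), and reporting of losses by group with reasons.

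The cost is wording and a little analysis work, with no extra participants. The change can still be applied to data already collected. The main gain is that the randomised groups are kept and robustness can be tested; how much imputation adds depends on which baseline variables were recorded. The as-randomised effect may also be smaller than the effect among adherers. If 5–20% of the robot arm gained nothing (an assumption), d = 0.5 would become 0.5 × 0.95 = 0.475 to 0.5 × 0.80 = 0.40. That dilution is part of the effect of offering the intervention, and is no reason to exclude those women.

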## 4. Significance Level

Two-tailed tests with  $\alpha = 0.05$ .
